### 10.3. Sample Size and Power Considerations

A standard 3+3 design ([Storer, 1989](#)) will be used for dose escalation as described in Section [4.1](#), and approximately 15 subjects will be enrolled. Sample sizes are not based on statistical calculation but rather on clinical empirical and practical considerations traditionally used for phase 1 studies of this kind.

### 10.4. Background and Demographic Characteristics

Subjects' age, height, weight, and baseline characteristics will be summarized using descriptive statistics, while gender, race and other categorical variables will be provided using frequency tabulations. Medical history data will be summarized using frequency tabulations by system organ class and preferred term. The treated population will be used to summarize background and demographic characteristics.

### 10.5. Subject Disposition

Subject disposition (analysis population allocation, entered, discontinued, along with primary reason for discontinuation) will be summarized using frequency and percent for both treatment and follow-up periods. A summary of subjects enrolled by site will be provided. Protocol

deviations will be summarized using frequency tabulations. The enrolled population will be used to summarize subject disposition.

## **10.6. Efficacy Analysis**

The efficacy population will be used for efficacy analysis. The efficacy variables of primary interest are tumor response. Tumor response (Appendix A, Section 19.1) will be based on investigator assessment using the Response Evaluation Criteria In Solid Tumors (RECIST) version 1.1 for solid tumors, and the International Workshop Group (IWG) Revised Criteria for Lymphoma. Subjects will be evaluated for tumor response on Day 15 of Cycle 2, 4, 6, and every 3 cycles thereafter. A descriptive analysis of evidence of antitumor activity will be provided based on clinical, laboratory and radiographic assessments performed by the investigator, which includes assessments of target lesions, non-target lesions, new lesions and overall response. Both confirmed and unconfirmed responses by RECIST version 1.1 will be assessed.

The efficacy variable of focus will be best overall response. Duration of response will also be assessed. The data analyses of other preliminary efficacy variables will be detailed in the Statistical analysis plan (SAP).

## **10.7. Safety Analysis**

All subjects who receive at least one dose of study medication will be included in the safety analyses. Adverse events, vital sign measurements, physical examination findings, clinical laboratory information, ECG interpretations, LVEF assessments and concomitant medications will be tabulated and summarized by dose level, visit cycle, and tumor type, as appropriate.

DLTs and all available safety information will be reviewed on an ongoing basis by the investigators and sponsor and summarized at the conclusion of each dose level. After completion of each dose cohort, the SRC will review the summarized data to determine the next step. Complete safety data for the DLT evaluation period will be summarized when all subjects have completed the DLT evaluation period.

Adverse events observed will be classified using the MedDRA classification system. The severity of toxicities will be graded according to NCI CTCAE version 4.03 whenever possible.

The frequency of adverse events will be tabulated by MedDRA System Organ Class and Preferred Term. In the by-subject analysis, a subject experiencing the same event more than once will only be counted once. Adverse events will be summarized by NCI CTCAE grade. Adverse events leading to discontinuation from treatment, events classified as Grade 3 or higher, treatment-related events, serious adverse events, and deaths will be tabulated and listed separately. Subject listings of all adverse events, serious adverse events, and their attributes will be provided.

Clinical laboratory data will be summarized. Lab data will be graded according to NCI CTCAE version 4.03 whenever possible. The frequencies of the worst severity grade observed during treatment will be displayed in cross-tabulations by screening status.

Vital signs, ECG data and LVEF data will be summarized by cross-tabulations presenting normal and abnormal values by number of subjects at pre- and post-IP initiation.

Graphical displays will be provided where useful in the interpretation of results.

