**Table 3: Table of Events (Continued)**

Test and Observations	Reference Section	Screening		Treatment cycles (28 days)												End of treatment	Follow-up
				Cycle 1						Cycle 2 to 4				Subsequent Cycles			
Visit (Allowable window)		Within 28 days of Cycle 1 Day 1	Within 7 days of Cycle 1 Day 1	Day 1	Day 2	Day 8 (± 2 days)	Day 10, 11 or 12	Day 11, 12 or 13	Day 15 (± 2 days)	Day 22 (± 2 days)	Day 1 (± 2 days) a	Day 8 (± 2 days)	Day 15 (± 2 days)	Day 22 (± 2 days)	Day 1 (± 3 days)	Within 21 days of last dose	28 days after last dose (+ 7 days)
Assessment of hydration status	6.2.1	X		X		X			X	X	X	X	X	X	X		
Height	6.2.1	X															
Weight	6.2.1	X		X		X			X	X	X	X	X	X	X	X	
Vital signs	6.2.2	X		X		X			X	X	X	X	X	X	X	X	
Serum β-HCG pregnancy test (for FCBP only) c	6.2.4	X c		As clinically indicated													
Urine β-HCG pregnancy test (for FCBP only) c	6.2.4			X		X			X	X	X				X	X	X
Amylase, lipase	6.2.6		X								X				X	X	
Cholesterol & TG	6.2.6		X								X				X	X	
TSH, fT4, LDH	6.2.6		X								X				X	X	
Immunoglobulins & T cell subsets (CD4+, CD8+)	6.2.6		X								X				X	X	
Uric acid	6.2.6		X								X				X	X	
Troponin-T, BNP	6.2.6		X	X d		X			X	X	X				X	X	
Hematology with differential	6.2.6		X	X d		X	X		X	X	X	X	X	X	X	X	
Biochemistry	6.2.6		X	X d		X			X	X	X	X	X	X	X	X	
Coagulation	6.2.6		X	X d		X			X	X	X	X	X	X	X	X	
Urinalysis	6.2.6	X		X d							X				X	X	
HBsAg & HCV RNA	6.2.6	X															

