- b After completion of Cycle 1, written informed consent will be obtained again from subjects prior to the start of the second cycle of treatment.
- c As per the PPRMP, screening pregnancy tests must be performed within 10 to 14 days prior to starting dosing. FCBP with regular or no menstrual cycles will undergo postdose pregnancy tests as noted on this table, every week for the first 28 days and every 28 days thereafter until the end of treatment, and 28 days after the last dose of CC-122. However, FCBP with irregular menstrual cycles will undergo weekly assessments for the first 28 days, every 14 days thereafter until the end of treatment and the end of treatment pregnancy test must be performed 14 and 28 days after discontinuing treatment.
- d If screening assessments are performed within 2 days of Cycle 1 Day 1 these assessments do not need to be repeated on Cycle 1 Day 1.
- e Triplicate ECGs (3 recordings within  $2\pm 1$  minute intervals) will be performed only at screening. Single ECGs will be collected for all other visits.
- f During the study, LVEF assessments should be repeated on Day 1 after every three cycles starting with Cycle 3 and when clinically indicated (for example, for decreased cardiac output) using the same modality at screening.
- g Ophthalmology examinations will be performed for all subjects at screening and during the study if clinically indicated.
- h Tumor assessments include imaging studies (via CT/MRI) and may include brain scans, and/or bone marrow aspirate/biopsy depending on tumor type and involvement. After screening, tumor assessments will be performed on Day 15 of Cycle 2, 4, 6 and every 3 cycles thereafter (Cycles 9, 12, 15, etc.), with an allowable window of  $\pm 7$  days. Tumor assessments at the end of treatment visit may be omitted if performed within the previous 28 days.
- i Refer to Section 6.4 for details on PK sampling time points.
- j Starting from Cycle 1 Day 1, CC-122 is administered once a day for 5 continuous days out of 7 days per week.
- k If performed on Day 13, a dose of CC-122 will not be administered.

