#### **6.2.6. Clinical Laboratory Tests**

The following clinical laboratory tests will be assessed. All samples should be drawn predose unless otherwise specified. Data will be captured in the source documents and the CRF.

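### The laboratory shift tables take screening as the reference even where a later predose Cycle 1 Day 1 value is scheduled

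*Combined protocol and SAP*

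**What the plan says.** Section 10.7 grades laboratory data by CTCAE 4.03 where possible and then specifies the shift table: "The frequencies of the worst severity grade observed during treatment will be displayed in cross-tabulations by screening status". It defines neither screening status nor a laboratory baseline. Nor does it say when the on-treatment interval begins.

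For vital signs, ECG and LVEF the next paragraph of the same section uses a different reference: "cross-tabulations presenting normal and abnormal values by number of subjects at pre- and post-IP initiation".

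Three other places determine which pretreatment values exist:

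- Table 3 puts the screening draw for most laboratory rows in the column "Within 7 days of Cycle 1 Day 1". Urinalysis is in the 28-day column.
- Table 3 adds a Cycle 1 Day 1 draw for five rows, among them "Hematology with differential". Footnote d qualifies it: "If screening assessments are performed within 2 days of Cycle 1 Day 1 these assessments do not need to be repeated".
- Section 6.2.6 fixes the time of the draw: "All samples should be drawn predose unless otherwise specified".

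Section 4.3 starts the treatment period on Cycle 1 Day 1, and Table 3 lists that visit under the treatment cycles.

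**The concern.** A shift table should compare a subject's state just before the drug with the worst state after it. For five panels the schedule provides that value on Day 1, but the analysis uses an older one. Whatever moves between screening and the first dose is then shown as if it happened under CC-122. This could be the disease, recovery from earlier treatment, or drift after screening values that were required to meet the eligibility limits.

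The Day 1 draw raises a second problem. It precedes any CC-122 but falls on a day that the protocol assigns to the treatment period. A programmer following the text could take a predose result as the worst on-treatment grade.

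What is at stake is the by-dose description of laboratory toxicity. Hematology matters most: Section 1.1.3 reports Grade 3 or 4 neutropenia in 64.0% of the earlier NHL 3 mg daily cohort and 30.6% of the DLBCL-2 cohort on 4 mg 5/7 days. With cohorts of 3 to 6, a single subject is visible in the table.

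**Working it through.** The plan states no figure on this point, so there is none to reproduce. The check compares Section 10.7 with the visit schedule.

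**Step 1. Which rows are exposed.** Table 3 has ten laboratory rows that are repeated during the study (leaving aside pregnancy and hepatitis tests).

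| Row | Screening window | Day 1 draw |
|---|---|---|
| Troponin-T, BNP | 7 days | yes, footnote d |
| Hematology | 7 days | yes, footnote d |
| Biochemistry | 7 days | yes, footnote d |
| Coagulation | 7 days | yes, footnote d |
| Urinalysis | 28 days | yes, footnote d |
| Amylase, lipase | 7 days | no |
| Cholesterol, triglycerides | 7 days | no |
| TSH, fT4, LDH | 7 days | no |
| Immunoglobulins, T cell subsets | 7 days | no |
| Uric acid | 7 days | no |

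Exposed: 5 of 10. For the other five, screening is the only scheduled pretreatment value.

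**Step 2. How long the gap is.** Footnote d removes the Day 1 draw when screening was 2 days or less before dosing, and screening is then the last predose value. Where the draw is required, the gap is 3 to 7 days for four panels and 3 to 28 days for urinalysis. A Day 1 sample drawn although the footnote waived it would also be affected, over 2 days or less.

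**Step 3. What the two rules show.** The grades below are hypothetical, for one subject and one test.

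| Screening | Predose Day 1 | Worst after first dose | Current rule, Day 1 not counted | Current rule, Day 1 counted | Last-predose rule |
|---|---|---|---|---|---|
| 0 | 1 | 1 | 0 to 1 | 0 to 1 | 1 to 1 |
| 0 | 1 | 0 | 0 to 0 | 0 to 1 | 1 to 0 |
| 2 | 1 | 1 | 2 to 1 | 2 to 1 | 1 to 1 |

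Row 1 shows a worsening that was complete before dosing. Row 2 shows a worsening only if the predose value is counted as on treatment. Row 3 shows an improvement that came before the drug.

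**Step 4. How often this could occur.** Let q be the share of subjects whose grade for a given test differs between screening and predose Day 1. The documents do not give q, so the values below are assumptions. Section 10.3 says that "approximately 15 subjects will be enrolled". With n subjects, the expected number is n × q, and the chance of at least one is 1 − (1 − q)^n.

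| Assumed q | Expected of 15 | At least 1 of 15 | At least 1 of 6 | At least 1 of 3 |
|---|---|---|---|---|
| 2% | 0.30 | 0.261 | 0.114 | 0.059 |
| 5% | 0.75 | 0.537 | 0.265 | 0.143 |
| 10% | 1.50 | 0.794 | 0.469 | 0.271 |
| 20% | 3.00 | 0.965 | 0.738 | 0.488 |

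For example, at q = 5% and n = 15, 1 − 0.95^15 = 0.537. These figures treat every subject as having both samples, so they are upper values for a given q: some subjects will have screening within 2 days and no repeat. They count differing grades; a difference changes the table only where the starting category or the worst grade changes with it.

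**Step 5. Weight of one subject.** 1/3 = 33 percentage points in a cohort of 3 and 1/6 = 17 points in a cohort of 6. This is the weight of any one subject in such a cohort, not an estimate of the error.

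**The case against.** The strongest reply is that the wording is loose but the consequence is small and conditional. A shift is displaced only if the panel has a Day 1 sample, screening was more than 2 days earlier, the two grades differ, and the difference shows in the table. For four of the five panels the gap is at most a week. All of this stands, and it is why the point concerns what can be shown, not what will be.

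A reader might infer that carry-over from prior therapy contaminates the toxicity picture, because exclusion 6 permits entry 5 half-lives after earlier treatment. The documents do not support going that far. The washout is the shorter of 5 half-lives and 4 weeks, and the same criterion excludes anyone who has not recovered from side effects of that therapy. Section 7.2 adds limits on blood counts and on liver and kidney tests. These narrow the mechanism without ruling it out.

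A reader might also infer that dose decisions are at risk. They are not tied to this table: Sections 8.2.5 to 8.2.8 rest on counts of subjects with DLTs and on the MTD from global studies, and Table 8 defines the DLTs. Section 10.7 also provides for laboratory summaries by visit cycle where appropriate, so the shift table is not the only display.

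Finally, the protocol refers to a separate SAP, which is not in the text available here and may define baseline. Screening status may also be meant loosely as pretreatment status, since footnote d treats the Day 1 draw as a repeat of screening. Neither possibility can be excluded. But Section 10.6 defers only other efficacy variables to the SAP, and Section 10.7 makes no such deferral for laboratory data. As written, the rule names screening.

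**Conclusion.** The point holds as a minor matter of analysis definition. For five of ten repeated laboratory rows, Section 10.7 passes over the last value before the first dose and leaves open whether that value counts as on treatment. A grade change before dosing can therefore be tabulated as a shift under CC-122, in either direction. The same section already uses the start of study drug as the dividing line for vital signs, ECG and LVEF.

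The size is unknown. It depends on q, which the documents do not give; over assumed values of 2% to 20%, between 0.3 and 3 of 15 subjects would be expected to have differing grades for a given test. It would be wrong to infer that all laboratory panels are affected, that misattribution is certain, or that 33 or 17 percentage points measures the bias.

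The conclusion rests on two assumptions: that screening status means the screening-visit value, and that no SAP text overrides it.

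**What to change.** In Section 10.7, replace the reference to screening status with: *by baseline grade, defined for each test as the last value before the first dose of CC-122 (predose Cycle 1 Day 1 if drawn, otherwise screening)*. Add: *on-treatment values are those obtained after the first dose*.

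The words *if drawn, otherwise screening* are needed. A rule tied only to footnote d would leave no baseline source for the five rows without a Day 1 sample, or for a subject whose Day 1 sample is missing. With this wording, the result differs from the current rule only where a Day 1 value exists.

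The cost is a short text change and a baseline flag in programming. It needs no new samples or visits, and it brings the laboratory tables into line with the rest of the section.

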## **10.8. Interim Analysis**

No formal interim analysis is planned.

## **10.9. Assessment of Pharmacokinetics**

Pharmacokinetic measures are incorporated into the study to assess the extent of systemic exposure, provided data is sufficient. Blood samples for PK will be collected at selected visits from all subjects. The following PK measurements will be determined for CC-122 after doses of CC-122 are given:

- Area under the plasma concentration time-curve (AUC).
- Peak (maximum) plasma concentration ( $C_{\max}$ ).
- Terminal half-life of ( $t_{1/2}$ ).
- Time to maximum plasma concentration ( $T_{\max}$ ).
- Apparent clearance (CL/F).
- Apparent volume of distribution (Vz/F).

Descriptive statistics (N, mean, standard deviation [SD], coefficient of variation [CV%], standard error [SE], geometric mean, geometric CV%, median, min, and max) will be provided for all data. Results will be presented in tabular and graphic forms as appropriate.

## 11. ADVERSE EVENTS

### 11.1. Monitoring, Recording and Reporting of Adverse Events

An adverse event is any noxious, unintended, or untoward medical occurrence that may appear or worsen in a subject during the course of a study. It may be a new intercurrent illness, a worsening concomitant illness, an injury, or any concomitant impairment of the subject's health, including laboratory test values (as specified by the criteria in Section 11.3), regardless of etiology. Any worsening (such as any clinically significant adverse change in the frequency or intensity of a preexisting condition) should be considered an AE. A diagnosis or syndrome should be recorded on the AE page of the CRF rather than the individual signs or symptoms of the diagnosis or syndrome.

Abuse, withdrawal, sensitivity or toxicity to an investigational product should be reported as an AE. Overdose, accidental or intentional, whether or not it is associated with an AE should be reported on the overdose CRF. (See Section 8.2.9.5 for the definition of overdose.) Any sequela of an accidental or intentional overdose of an investigational product should be reported as an AE on the AE CRF. If the sequela of an overdose is an SAE, then the sequelae must be reported on an SAE report form and on the AE CRF. The overdose resulting in the SAE should be identified as the cause of the event on the SAE report form and CRF but should not be reported as an SAE itself.

All subjects will be monitored for AEs during the study. Assessments may include monitoring of any or all of the following parameters: the subject's clinical symptoms, laboratory, pathological, radiological or surgical findings, physical examination findings, or findings from other tests and/or procedures.

All AEs will be recorded by the investigator from the time the subject signs informed consent until 28 days after the last dose of IP and those SAEs made known to the investigator at any time thereafter that are suspected of being related to IP. AEs and serious adverse events will be recorded on the AE page of the CRF and in the subject's source documents. All SAEs must be reported to Celgene Drug Safety within 24 hours of the investigator's knowledge of the event by facsimile, or other appropriate method, using the SAE Report Form, or approved equivalent form.

### 11.2. Evaluation of Adverse Events

A qualified investigator will evaluate all adverse events as to:

#### 11.2.1. Seriousness

An SAE is any AE occurring at any dose that:

- Results in death;
- Is life-threatening (in the opinion of the investigator, the subject is at immediate risk of death from the AE);

- Requires inpatient hospitalization or prolongation of existing hospitalization (hospitalization is defined as an inpatient admission, regardless of length of stay);
- Results in persistent or significant disability/incapacity (a substantial disruption of the subject's ability to conduct normal life functions);
- Is a congenital anomaly/birth defect;
- Constitutes an important medical event.

Important medical events are defined as those occurrences that may not be immediately life threatening or result in death, hospitalization, or disability, but may jeopardize the subject or require medical or surgical intervention to prevent one of the other outcomes listed above. Medical and scientific judgment should be exercised in deciding whether such an AE should be considered serious.

Events **not considered** to be SAEs are hospitalizations for:

- A standard procedure for protocol therapy administration. However, hospitalization or prolonged hospitalization for a complication of therapy administration will be reported as an SAE.
- Routine treatment or monitoring of the studied indication not associated with any deterioration in condition.
- The administration of blood or platelet transfusion as routine treatment of studied indication. However, hospitalization or prolonged hospitalization for a complication of such transfusion remains a reportable SAE.
- A procedure for protocol/disease-related investigations (such as surgery, scans, endoscopy, sampling for laboratory tests, bone marrow sampling). However, hospitalization or prolonged hospitalization for a complication of such procedures remains a reportable SAE.
- Hospitalization or prolongation of hospitalization for technical, practical, or social reasons, in absence of an AE.
- A procedure that is planned (planned prior to starting of treatment on study); must be documented in the source document and the CRF. Hospitalization or prolonged hospitalization for a complication remains a reportable SAE.
- An elective treatment of or an elective procedure for a preexisting condition unrelated to the studied indication.
- Emergency outpatient treatment or observation that does not result in admission, unless fulfilling other seriousness criteria above.

If an AE is considered serious, both the AE page/screen of the CRF and the SAE Report Form must be completed.

For each SAE, the investigator will provide information on severity, start and stop dates, relationship to IP, action taken regarding IP, and outcome.

### **11.2.2. Severity/Intensity**

For both AEs and SAEs, the investigator must assess the severity/intensity of the event.

The severity/intensity of AEs will be graded based upon the subject's symptoms according to the current active minor version of CTCAE version 4.03.

[http://www.jcog.jp/doctor/tool/CTCAEv4J\\_20111217.pdf](http://www.jcog.jp/doctor/tool/CTCAEv4J_20111217.pdf)

AEs that are not defined in the CTCAE should be evaluated for severity/intensity according to the following scale:

- Grade 1 = Mild – transient or mild discomfort; no limitation in activity; no medical intervention/therapy required
- Grade 2 = Moderate – mild to moderate limitation in activity, some assistance may be needed; no or minimal medical intervention/therapy required
- Grade 3 = Severe – marked limitation in activity, some assistance usually required; medical intervention/therapy required, hospitalization is possible
- Grade 4 = Life-threatening – extreme limitation in activity, significant assistance required; significant medical intervention/therapy required, hospitalization or hospice care probable
- Grade 5 = Death - the event results in death

The term “severe” is often used to describe the intensity of a specific event (as in mild, moderate or severe myocardial infarction); the event itself, however, may be of relatively minor medical significance (such as severe headache). This criterion is *not* the same as “serious,” which is based on subject/event *outcome* or *action* criteria associated with events that pose a threat to a subject’s life or functioning.

Seriousness, not severity, serves as a guide for defining regulatory obligations.

